**Table 1-2 Summary of Key Issues, Their Impact and Strategy to Mitigate Risk**

Potential risk	Summary of data	Impact- eligibility criteria	Strategy-monitoring
Post-injection systemic reactions and Hypersensitivity	Administration of belimumab may result in infusion and hypersensitivity reactions, which can be severe and can be fatal. Non-serious infusion reactions and hypersensitivity reactions are common in SLE clinical trials with IV belimumab. Serious infusion and hypersensitivity reactions affected less than 1% of patients and included anaphylactic reaction, bradycardia, hypotension, angioedema, and dyspnea. Delays in the onset of hypersensitivity reactions have been observed. Infusion reactions following administration of belimumab occurred more frequently on the first 2 infusion days and tended to decrease with subsequent administrations. Delayed-type, non-acute hypersensitivity reactions have also been observed and included symptoms such as rash, nausea, fatigue, myalgia, headache, and facial oedema.	Exclusion of subjects with a history of an anaphylactic reaction to parenteral administration of contrast agents, human or murine proteins or monoclonal antibodies.	Subjects should remain under clinical supervision for 3 hours after completion of the first 2 infusions. Should symptoms of acute hypersensitivity occur, an extended period of monitoring may be appropriate, based on clinical judgment. Otherwise, subjects will be monitored during and after each infusion according to study sites' guidelines or standard operating procedure for IV infusions. This may include, but is not limited to, monitoring vital signs and observing for any untoward reactions. Subjects should be made aware of the potential risk, the signs and symptoms of such reactions, and the importance of immediately seeking medical attention. Belimumab should be administered by a healthcare professional prepared to treat hypersensitivity reactions including anaphylaxis.
Infections	Infections occurred in a slightly greater proportion of subjects treated with belimumab compared with placebo. Infections occurring in at least 3% of patients receiving belimumab and at least 1% more frequently than patients receiving	Exclude patients with any of the following: currently on any suppressive therapy for a chronic infection; hospitalization for treatment of an infection within 60 days of Day 0; use of IV or IM	Monitor patients for signs and symptoms of infection, monitor laboratory values, request that patients report signs of infection. Treat infections immediately and appropriately.

Potential risk	Summary of data	Impact- eligibility criteria	Strategy-monitoring
	placebo were nasopharyngitis, bronchitis, pharyngitis, cystitis, and gastroenteritis viral. Serious infections occurred in 5% of patients receiving either belimumab or placebo.	antibiotics within 60 days of Day 0; a history of or positive test at screening for HIV, hepatitis B or hepatitis C; have Grade 3 or 4 lymphopenia; or have Grade 3 or 4 IgG or IgA deficiency	
Progressive multifocal leukoencephalopathy (PML)	No association between belimumab and the risk of opportunistic infections, including PML, has been indentified to date, but data are limited. PML resulting in neurological deficits, including fatal cases, has been reported in SLE patients receiving immunosuppressant pharmacotherapy, including belimumab.		A diagnosis of PML should be considered in any subject presenting with new-onset or deteriorating neurological signs and symptoms. The subject should be referred to a neurologist or other appropriate specialist for evaluation. If PML is confirmed, study agent should be discontinued and consideration should be given to stopping immunosuppressant therapy. If PML is suspected, this should be immediately reported to the Medical Monitor. The appropriateness of continuing study agent, while the case is being assessed, should be discussed.
Malignancies	As with other immunomodulating agents, the mechanism of action of belimumab may increase the potential risk for the development of malignancies.	Exclude patients with a history of malignant neoplasm within the last 5 years, except for adequately treated basal or squamous cell cancers of the skin, or carcinoma in situ of the uterine cervix.	Monitor patients for signs and symptoms of malignancy, monitor laboratory values, request that patients report signs and symptoms. Treat appropriately.
Immunogenecity	As with other monoclonal antibodies, treatment with belimumab could lead to the development of anti-drug antibodies		Monitor anti-drug antibody laboratory values.

Potential risk	Summary of data	Impact- eligibility criteria	Strategy-monitoring
	(ADA). Among SLE subjects treated with belimumab, the proportion of subjects who developed persistently positive ADA was low and very few of the persistently positive antibodies were found to be neutralizing. Neither development of ADA nor persistent ADA was associated with infusion or hypersensitivity reactions. As expected, the proportions of subjects with persistent ADA increased slightly over time in belimumab-treated subjects but (there was no increase in the number of subjects with neutralizing antibodies or the number reporting infusion-related adverse events.		
Effects on immunizations including reactions with live vaccines	No data are available on the secondary transmission of infection from persons receiving live vaccines to patients receiving belimumab. Because of its mechanism of action, belimumab may interfere with the response to immunisations. The efficacy of concurrent vaccination in patients receiving belimumab is not known. Limited data suggest that belimumab does not significantly affect the ability to maintain a protective immune response to immunisations received prior to administration of belimumab.	Exclude patients who have received a live vaccine within 30 days of Day 0.	Do not administer live vaccines concurrently.
Potential	There have been reports of depression	Exclude patients who have	Monitor patients for signs and symptoms of

Potential risk	Summary of data	Impact- eligibility criteria	Strategy-monitoring
psychiatric events - Depression and suicidality	and suicidality in patients receiving belimumab. The estimated rates of suicidality for belimumab remain consistent with the rates of the background SLE population. The background rate for completed suicide identified in the literature ranged from 0.02 to 2.18 per 100 PY and varied by study type (clinical trial or observational study) [ Li-Yu 2007 ; Cervera 2003 ; Cervera 2006 ; Cervera 2009 ]. The background rate for suicidal behavior (completed suicide and attempts) is 0.12 (95% CI 0.05, 0.24)/100 patient years [ Karassa 2003 ].	evidence of serious suicide risk including any history of suicidal behaviour in the last 6 months and/or any suicidal ideation of type 4 or 5 on the Columbia Suicide Severity Rating Scale [C-SSRS in the last 2 months or who in the investigator's judgment, pose a significant suicide risk.	psychiatric events including depression and suicidality, request that patients report signs and symptoms. Treat appropriately

Refer to Section 8.3 for information about the Independent Data Monitoring Committee (IDMC) being used in the study.

#### **1.4.2. Benefit Assessment**

The primary data supporting efficacy of belimumab were the Phase 3 trials (C1056 and C1057) in which 1,684 subjects were treated for up to 52 weeks (C1057) or 76 weeks (C1056) (Belimumab IB, Section 5.3.1.2). Belimumab produced significant improvements in the SLE Responder Index as well as in individual component SELENA-SLEDAI score in both studies. Pooled analyses demonstrated steroid sparing, delay in median time to first flare, and decreased risk of severe flares over 52 weeks. Clinical trial data for belimumab since approval continue to show efficacy in the treatment of SLE through decreased SLE flares and decreased disease activity across multiple organ systems (Belimumab IB, Section 5.3.1.3).

#### **1.4.3. Overall Benefit:Risk Conclusion**

The safety profile of belimumab remains consistent with that known at approval and is consistent with expected events based on the mechanism of action and the disease under study. Appropriate risk mitigation measures are in place; rare and long-term risks will be further evaluated via the large safety study and registry, ongoing and future studies, and routine pharmacovigilance. Review of safety data is conducted on a continual basis in order to identify new safety signals which may arise from clinical trial and/or post-marketing reports. The benefit: risk profile of belimumab for SLE continues to be favorable.

## **2. STUDY OBJECTIVES**

- To evaluate the efficacy of belimumab in adult SLE subjects of black race.
- To evaluate the safety and tolerability of belimumab in adult SLE subjects of black race.

## **3. STUDY DESIGN**

This is a Phase 3/4, multi-center, international, randomized, double-blind, placebo-controlled, 52-week study to evaluate the efficacy and safety of belimumab in adult black subjects with active SLE. Approximately 501 SLE subjects will be randomized with a target of at least 334 subjects treated with belimumab and 167 subjects receiving placebo.

In addition to receiving stable standard therapy, subjects will be randomized in a 2:1 ratio to treatment with either 10 mg/kg belimumab or placebo. At randomization, subjects will be stratified by their screening SELENA SLEDAI score (8-9 vs  $\geq 10$ ), complement level (C3 and/or C4 low vs other), and region (US/Canada vs rest of the world). Subjects will be dosed with study agent on Days 0, 14, 28, and then every 28 days through 48 weeks, with a final evaluation at Week 52 (4 weeks after the last dose). Study agent will be administered IV over no less than 1 hour. Subjects will remain under clinical supervision

for 3 hours after completion of the first 2 infusions during the 52-week double-blind phase and 6-month open-label extension.

All subjects will continue the stable standard therapy they were receiving during the screening period. Subjects who complete dosing up to 48 weeks will return for a Day 364/Week 52 (final evaluation) visit. Subjects who successfully complete the initial 52 week double-blind phase may enter into a 6-month open-label extension. The Day 364/Week 52 visit will serve as the Day 0 visit for subjects entering the 6-month open-label extension. Subjects on active drug or placebo will receive belimumab 10 mg/kg IV every 28 days for 6 months in the open-label extension. The 1st dose on the 6-month open-label extension will be given on Day 364 (Week 52) of the double-blind treatment phase following the completion of all Day 364 (Week 52) assessments. Subjects participating in the 6-month open-label extension will continue to be monitored for safety and more latitude will be permitted for background medication changes as outlined in Section 5.5. Subjects who complete the 52-week double-blind phase, but do not enter the 6-month open-label extension will be required to return for an additional follow up visit 8 weeks after the last dose of study agent. Subjects who withdraw early will be required to return for an Exit visit (4 weeks after the last dose of study agent) and a follow-up visit approximately 8 weeks after their last dose of study agent. The 8-week follow up visit is not required for subjects entering the separate continuation protocol. In the event that a subject discontinues study agent at any time during the study or withdraws consent, an attempt will be made to ascertain survival status approximately 52 weeks after the first dose of study agent.

At the end of the 6-month open-label period, subjects who wish to continue treatment may do so by being prescribed commercially available product. If belimumab is not commercially available in a subject's country of participation, subjects may continue to receive belimumab under a separate continuation protocol. A separate informed consent will need to be provided for the continuation protocol.

## **4. INCLUSION AND EXCLUSION CRITERIA**

### **4.1. Inclusion Criteria**

Subjects enrolled in the study must meet the following inclusion criteria:

1. Are at least 18 years of age.
2. Are self-identified black race.
3. Have a clinical diagnosis of SLE according to the American College of Rheumatology (ACR) criteria (see [Appendix 1](#)).
4. Have active SLE disease defined as a SELENA SLEDAI score  $\geq 8$  at screening (refer to [Appendix 5](#) and Section 6.8.1.1 Scoring for Proteinuria for Eligibility at Screening).
5. Have 2 unequivocally positive autoantibody test results defined as a positive antinuclear antibody (ANA) test [ie, titer  $\geq 1:80$  by HEp-2 immunofluorescence assay (IFA) and/or positive enzyme immunoassay (EIA)] and/or a positive anti-dsDNA ( $\geq 30$  IU/mL) serum antibody test as follows:

- from 2 independent time points within the study screening period. Screening results must be based on the study's central laboratory results.

OR

- One positive historical test result and 1 positive test result during the screening period.  
Historical documentation of a positive ANA test (eg, HEp-2 IFA or EIA) or anti-dsDNA (eg, anti-dsDNA by any validated commercial assay) must include the date and type of the test, the name of the testing laboratory, numerical reference range, and a key that explains values provided as positive vs negative OR negative, equivocal/borderline positive). Only unequivocally positive values as defined in the laboratory's reference range are acceptable; borderline values will not be accepted.

6. Are on a stable SLE treatment regimen consisting of any of the following medications (alone or in combination) for a period of at least 30 days prior to Day 0 (ie, day of 1st dose of study agent) [Refer to Section [5.5.1](#) for allowable medications and maximum dose]:

- Corticosteroids (prednisone or prednisone equivalent, up to 40 mg/day):
  - For subjects on SLE combination therapy, their stable steroid dose must be fixed within the range of 0 to 40 mg/day (prednisone or prednisone equivalent).
  - For subjects whose only SLE treatment is steroids, their stable steroid dose must be fixed within the range of 7.5 to 40 mg/day (prednisone or prednisone equivalent).
  - For those subjects on alternating day doses of steroids, use the average of 2 daily doses to calculate the average daily steroid dose.
- Other immunosuppressive or immunomodulatory agents including methotrexate, azathioprine, leflunomide, mycophenolate (including mycophenolate mofetil, mycophenolate mofetil hydrochloride, and mycophenolate sodium), calcineurin inhibitors (eg, tacrolimus, cyclosporine), sirolimus, oral cyclophosphamide, 6-mercaptopurine, mizoribine, or thalidomide.
- Anti-malarials (eg, hydroxychloroquine, chloroquine, quinacrine).
- Non-steroidal anti-inflammatory drugs (NSAIDs).

**NOTE:**

- Pre-existing SLE medications must be stable for at least 30 days prior to Day 0.
- Corticosteroids may be added as new medication or their doses adjusted only up to 30 days prior to Day 0 (see Exclusion Criterion #6).
- New SLE therapy other than corticosteroids must not be added within 60 days of Day 0 (see Exclusion Criterion #5).

7. A female subject is eligible to enter the study if she is:

- Not pregnant or nursing;
- Of non-childbearing potential defined as

- pre-menopausal females with a documented tubal ligation, hysterectomy, documented hysteroscopic tubal occlusion procedure with follow-up confirmation of bilateral tubal occlusion, or documented bilateral oophorectomy or
- postmenopausal defined as 12 months of spontaneous amenorrhea with an appropriate clinical profile [eg, > 45 years, in the absence of hormone replacement therapy or other cause for amenorrhea]; in questionable cases obtain a blood sample for follicle stimulating hormone (FSH) and estradiol simultaneously to confirm. Diagnostic levels for FSH and estradiol vary by specific laboratories/assays;
- OR is of child-bearing potential with negative pregnancy test as determined by serum human chorionic gonadotrophin (hCG) test at screening and urine hCG test prior to dosing AND
  - Agrees to use one of the contraception methods listed in the protocol (see Section 4.3) for 2 weeks prior to the day of dosing to sufficiently minimize the risk of pregnancy at that point. Female subjects must agree to use contraception until 16 weeks following the last dose of study agent.
- OR has only same-sex partners, when this is her preferred and usual lifestyle.

8. Have the ability to understand the requirements of the study, provide written informed consent (including consent for the use and disclosure of research-related health information), and comply with the study protocol procedures (including required study visits).

## **4.2. Exclusion Criteria**

Subjects will be excluded from participating in the study if they meet any of the following exclusion criteria:

1. Have received treatment with anti-BLyS [belimumab] at any time.
2. Have received any of the following within 364 days of Day 0:
  - Abatacept.
  - Other B cell targeted therapy (eg, rituximab, other anti-CD20 agents, anti-CD22 [epratuzumab], anti-CD52 [alemtuzumab], BLyS-receptor fusion protein [BR3], TACI-Fc, or anti-BAFF (LY2127399)).
  - A biologic investigational agent other than B cell targeted therapy (e.g., abetimus sodium, anti-CD40L antibody [BG9588/IDE-131]). (Investigational agent applies to any drug not approved for sale in the country in which it is being used.)
3. Have required 3 or more courses of systemic corticosteroids for concomitant conditions (eg, asthma, atopic dermatitis) within 364 days of Day 0. (Topical or inhaled steroids are permitted.)
4. Have received any of the following within 90 days of Day 0:
  - Anti-TNF therapy (eg, adalimumab, certolizumab pegol, etanercept, golimumab, infliximab).
  - Intravenous (IV) cyclophosphamide

- Interleukin-1 receptor antagonist (anakinra).
- Intravenous immunoglobulin (IVIG).
- High dose prednisone or equivalent (> 100 mg/day).
- Plasmapheresis.

5. Have received any of the following within 60 days of Day 0:

- A non-biologic investigational agent.
- Any new immunosuppressive/immunomodulatory agent, anti-malarial, or NSAID (see Inclusion Criterion #6).

Note: New inhaled and topical steroids and new topical immunosuppressive agents (eg, eye drops, topical creams) are allowed. Any NSAID use for < 1 week is allowed.

- Any steroid injection (eg, intramuscular, intraarticular, or intravenous).

6. Have received any of the following within 30 days of Day 0:

- A live vaccine.
- A change in dose of a corticosteroid, other immunosuppressive/immunomodulatory agent, anti-malarial, or NSAID (see Inclusion Criterion #6).

7. Have severe lupus kidney disease (defined by proteinuria > 6 g/24 hour or equivalent using spot urine protein to creatinine ratio, or serum creatinine > 2.5 mg/dL), or have severe active nephritis requiring acute therapy not permitted by protocol (eg, IV cyclophosphamide within 90 days of Day 0), or have required hemodialysis or high-dose prednisone (> 100 mg/day) within 90 days of Day 0.

8. Have severe active central nervous system (CNS) lupus (including seizures, psychosis, organic brain syndrome, cerebrovascular accident [CVA], cerebritis, or CNS vasculitis) requiring therapeutic intervention within 60 days of Day 0.

9. Have a history of a major organ transplant (eg, heart, lung, kidney, liver) or hematopoietic stem cell/marrow transplant.

10. Have clinical evidence of significant unstable or uncontrolled acute or chronic diseases not due to SLE (ie, cardiovascular, pulmonary, hematologic, gastrointestinal, hepatic, renal, neurological, malignancy, or infectious diseases) which, in the opinion of the principal investigator, could confound the results of the study or put the subject at undue risk.

11. Have a planned surgical procedure or a history of any other medical disease (eg, cardiopulmonary), laboratory abnormality, or condition (eg, poor venous access) that, in the opinion of the principal investigator, makes the subject unsuitable for the study.

12. Have a history of malignant neoplasm within the last 5 years, except for adequately treated cancers of the skin (basal or squamous cell) or carcinoma in situ of the uterine cervix.

13. Have required management of acute or chronic infections, as follows:

- Currently on any suppressive therapy for a chronic infection (such as tuberculosis, pneumocystis, cytomegalovirus, herpes simplex virus, herpes zoster, and atypical mycobacteria).
- Hospitalization for treatment of infection within 60 days of Day 0.

- Use of parenteral (IV or IM) antibiotics (antibacterials, antivirals, anti-fungals, or anti-parasitic agents) within 60 days of Day 0.

14. Subjects who have evidence of serious suicide risk including any history of suicidal behavior in the last 6 months and/or any suicidal ideation of type 4 or 5 on the screening Columbia-Suicide Severity Rating Scale (C-SSRS) (refer to [Appendix 3](#) for baseline/screening C-SSRS) in the last 2 months or who, in the investigator's opinion, pose a significant suicide risk.

15. Have current drug or alcohol abuse or dependence, or a history of drug or alcohol abuse or dependence within 364 days prior to Day 0.

16. Have a historically positive test or test positive at screening for HIV antibody, hepatitis B surface antigen (HBsAg), hepatitis B core antibody, or hepatitis C antibody.

17. Have an IgA deficiency (IgA level < 10 mg/dL).

18. Have a Grade 3 or greater laboratory abnormality based on the Adverse Event Severity Grading Tables ([Appendix 12](#)) except for the following that are allowed:

- Stable Grade 3 prothrombin time (PT) secondary to anticoagulant, eg, warfarin, treatment.
- Stable Grade 3 partial thromboplastin time (PTT) due to lupus anticoagulant and not related to liver disease or anti-coagulant therapy.
- Stable Grade 3/4 proteinuria ( $\leq 6$  g/24 hour equivalent by spot urine protein to creatinine ratio allowed).
- Stable Grade 3 hypoalbuminemia due to lupus nephritis, and not related to liver disease or malnutrition.
- Stable Grade 3 gamma glutamyl transferase (GGT) elevation due to lupus hepatitis, and not related to alcoholic liver disease, uncontrolled diabetes, or viral hepatitis. If present, any abnormalities in ALT and/or AST must be  $\leq$  Grade 2.
- Stable Grade 3 hemoglobin reduction due to lupus.
- Stable Grade 3 neutropenia or stable Grade 3 white blood cell count.

19. Have a history of an anaphylactic reaction to parenteral administration of contrast agents, human or murine proteins, or monoclonal antibodies.

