Hypophosphatemia	2.0-2.4 mg/dL	1.5-1.9 mg/dL	1.0-1.4 mg/dL	< 1.0 mg/dL
Calcium- (Corrected For Albumin)				
Hypocalcemia	7.8-8.4 mg/dL	7.0-7.7 mg/dL	6.1-6.9 mg/dL	< 6.1 mg/dL
Hypercalcemia	10.6-11.5 mg/dL	11.6-12.5 mg/dL	12.6-13.5 mg/dL	>13.5 mg/dL
Magnesium				
Hypomagnesemia	1.2-1.4 meq/L	0.9-1.1 meq/L	0.6-0.8 meq/L	< 0.6 meq/L
Albumin				
Hypoalbuminemia	3.00-3.49 g/dL	2.50-2.99 g/dL	2.00-2.49 g/dL	< 2.00 g/dL
Bilirubin (Total)				
Hyperbilirubinemia (Total)	> 1.0-1.5 x ULN	> 1.5-2.5 x ULN	> 2.5-5 x ULN	> 5 x ULN
Glucose				
Hypoglycemia	55-64 mg/dL	40-54 mg/dL	30-39 mg/dL	< 30 mg/dL
Hyperglycemia (nonfasting & no prior diabetes)	116-160 mg/dL	161-250 mg/dL	251-500 mg/dL	> 500 mg/dL
Triglycerides	151-399 mg/dL	400-750 mg/dL	751-1200 mg/dL	> 1200 mg/dL
Creatinine	> 1.0-1.5 x ULN	> 1.5-3.0 x ULN	> 3.0-6.0 x ULN	> 6.0 x ULN

(continued)

Modified from DMID Adult Toxicity Tables, 2001

CHEMISTRIES	GRADE 1 MILD	GRADE 2 MODERATE	GRADE 3 SEVERE	GRADE 4 POTENTIALLY LIFE-THREATENING
Uric Acid				
Hyperuricemia	7.5-10.0 mg/dL	10.1-12.0 mg/dL	12.1-15.0 mg/dL	> 15.0 mg/dL
Liver Transferases (AST, ALT, and GGT)	1.25-2.5 x ULN	> 2.5-5.0 x ULN	> 5.0-10.0 x ULN	> 10.0 x ULN
Alkaline Phosphatase	1.25-2.5 x ULN	> 2.5-5.0 x ULN	> 5.0-10.0 x ULN	> 10.0 x ULN
Pancreatic Enzymes				
Amylase	> 1.0-1.5 x ULN	> 1.5-2.0 x ULN	> 2.0-5.0 x ULN	> 5.0 x ULN
Pancreatic amylase	> 1.0-1.5 x ULN	> 1.5-2.0 x ULN	> 2.0-5.0 x ULN	> 5.0 x ULN
Lipase	> 1.0-1.5 x ULN	> 1.5-2.0 x ULN	> 2.0-5.0 x ULN	> 5.0 x ULN
Hypoglobulinemia (IgG)*	550-700 mg/dL	400-549 mg/dL	250-399 mg/dL	< 250 mg/dL

\*(Goldfarb et al, 2001; Yamani et al, 2001; Eibl and Rosen, 1995).

Modified from DMID Adult Toxicity Tables, 2001

(continued)

GASTROINTESTINAL	GRADE 1	GRADE 2	GRADE 3	GRADE 4
	MILD	MODERATE	SEVERE	POTENTIALLY LIFE-THREATENING
Nausea	Mild OR transient; reasonable intake maintained	Mod discomfort OR intake decreased for < 3 days	Severe discomfort OR minimal intake for ≥ 3 days	Hospitalization required
Vomiting	Mild OR transient; 2-3 episodes/day OR mild vomiting lasting < 1 week	Mod OR persistent; 4-5 episodes per day; OR vomiting lasting ≥ 1 week	Severe vomiting of all foods/fluids in 24 hours OR orthostatic hypotension OR IV treatment req	Hypotensive shock OR hospitalization required for IV treatment req

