### Phase III-IV liver chemistry stopping criteria and required follow up assessments

Liver Chemistry Stopping Criteria - Liver Stopping Event	
ALT-absolute	ALT $\geq$ 8xULN
ALT Increase	ALT $\geq$ 5xULN but $<8$ xULN persists for $\geq 2$ weeks ALT $\geq$ 3xULN but $<5$ xULN persists for $\geq 4$ weeks
Bilirubin	ALT $\geq$ 3xULN and bilirubin $\geq$ 2xULN ( $>35\%$ direct bilirubin)
INR^2	ALT $\geq$ 3xULN and INR $>1.5$ , if INR measured
Cannot Monitor	ALT $\geq$ 5xULN but $<8$ xULN and cannot be monitored weekly for $\geq 2$ weeks ALT $\geq$ 3xULN but $<5$ xULN and cannot be monitored weekly for $\geq 4$ weeks
Symptomatic	ALT $\geq$ 3xULN associated with symptoms (new or worsening) believed to be related to liver injury or hypersensitivity

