### Required Actions and Follow up Assessments following ANY Liver Stopping Event

Actions	Follow Up Assessments

• Immediately discontinue study treatment

• Report the event to GSK within 24 hours

• Complete the liver event CRF and complete an SAE data collection tool if the event also meets the criteria for an SAE

• Perform liver event follow up assessments

• Monitor the subject until liver chemistries resolve, stabilize, or return to within baseline (see MONITORING below)

• Do not restart/rechallenge subject with study treatment unless allowed per protocol and GSK Medical Governance approval is

	

• Viral hepatitis serology

• Only in those with underlying chronic hepatitis B at study entry (identified by positive hepatitis B surface antigen) quantitative hepatitis B DNA and hepatitis delta antibody

• Blood sample for pharmacokinetic (PK) analysis, obtained within approximately 1 to 2 weeks after the liver event

• Serum creatine phosphokinase (CPK) and lactate dehydrogenase (LDH)

• Fractionate bilirubin, if total

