### Phase III-IV liver chemistry increased monitoring criteria with continued therapy

Liver Chemistry Increased Monitoring Criteria – Liver Monitoring Event	
Criteria	Actions
ALT $\geq$ 5xULN and <8xULN and bilirubin <2xULN without symptoms believed to be related to liver injury or hypersensitivity, and who can be monitored weekly for 2 weeks.  OR  ALT $\geq$ 3xULN and <5xULN and bilirubin <2xULN without symptoms believed to be related to liver injury or hypersensitivity, and who can be monitored weekly for 4 weeks.	

• Notify the GSK medical monitor within 24 hours of learning of the abnormality to discuss subject safety.

• Subject can continue study treatment

• Subject must return weekly for repeat liver chemistries (ALT, AST, alkaline phosphatase, bilirubin) until they resolve, stabilise or return to within baseline

• If at any time subject meets the liver chemistry stopping criteria, proceed as described above

• If ALT decreases from ALT <math>\geq</math>5xULN and <8xULN to <math>\geq</math>3xULN but <5xULN, continue to monitor liver chemistries weekly.

• If, after 4 weeks of monitoring, ALT <3xULN and bilirubin <2xULN, monitor subjects twice monthly until liver chemistries normalize or return to within baseline.

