### ***Restart Following Transient Resolving Liver Stopping Events Not Related to Study Treatment***

Restart refers to resuming study treatment following liver stopping events in which there is a clear underlying cause (other than DILI) of the liver event (eg, biliary obstruction, pancreatic events, hypotension, acute viral hepatitis). Furthermore, there should be no evidence of alcoholic hepatitis or hypersensitivity, and the study treatment should not be associated with HLA markers of liver injury.

Approval by GSK for study treatment restart can be considered where:

- Investigator requests consideration for study treatment restart if liver chemistries have a clear underlying cause (e.g., biliary obstruction, hypotension and liver chemistries have improved to normal or are within 1.5 x baseline and ALT <3xULN).
- Restart risk factors (e.g. fever, rash, eosinophilia, or hypersensitivity, alcoholic hepatitis, possible study treatment-induced liver injury) or study treatment has an HLA genetic marker associated with liver injury (e.g. lapatinib, abacavir, amoxicillin/clavulanate) are reviewed and excluded.
- Ethics Committee or Institutional Review Board approval of study treatment restart must be obtained, as required.
- If restart of study treatment is approved by GSK Medical Governance in writing, the subject must be provided with a clear description of the possible benefits and risks of study treatment administration, including the possibility of recurrent, more severe liver injury or death.
- The subject must also provide signed informed consent specifically for the study treatment restart. Documentation of informed consent must be recorded in the study chart.
- Study treatment must be administered at the dose specified by GSK.
- Subjects approved by GSK Medical Governance for restarting study treatment must return to the clinic once a week for liver chemistry tests until stable liver chemistries have been demonstrated and then laboratory monitoring may resume as per protocol.

- If after study treatment re-start, subject meets protocol-defined liver chemistry stopping criteria, follow usual stopping criteria instructions.
- GSK Medical Monitor, and the Ethics Committee or Institutional Review Board as required, must be informed of the subject's outcome following study treatment restart.
- GSK to be notified of any adverse events, as per Section [7.2](#).

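### Criterion 18 admits ALT up to 5.0 × ULN, but Appendix 13 stops treatment, on its plain cell text, if ALT of 3 to <5 × ULN persists for 4 weeks

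*Protocol*

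**What the plan says.** **Entry.** Section 4.2, criterion 18, excludes subjects who "Have a Grade 3 or greater laboratory abnormality based on the Adverse Event Severity Grading Tables", with listed exceptions. One exception accepts stable Grade 3 GGT due to lupus hepatitis. On the transaminases it adds "If present, any abnormalities in ALT and/or AST must be" Grade 2 or lower, so Grade 2 ALT is accepted there in so many words. In Appendix 12, the chemistry row opening "Liver Transferases (AST, ALT, and GGT" sets Grade 2 at >2.5 to 5.0 × ULN and starts Grade 3 above 5.0 × ULN.

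**Stopping.** Appendix 13 lists as stopping events "ALT $\geq$ 3xULN but $<5$ xULN persists for $\geq 4$ weeks" and "ALT $\geq$ 5xULN but $<8$ xULN persists for $\geq 2$ weeks". The first required action is "Immediately discontinue study treatment". The increased-monitoring table lets an asymptomatic subject with ALT of 3 to <5 × ULN and bilirubin <2 × ULN keep dosing under weekly tests, but adds "If at any time subject meets the liver chemistry stopping criteria, proceed as described above".

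**Restart.** Appendix 14 offers one pathway, for transient, resolving events not related to treatment. It describes the state in which restart may be requested as one where "liver chemistries have improved to normal or are within 1.5 x baseline and ALT <3xULN"; that wording sits inside an illustrative parenthesis.

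**The concern.** The entry limit and the stopping limit use the same analyte and unit but were not set against each other. The Amendment 02 summary shows that the liver-safety section was replaced and Appendices 13 and 14 added in the same amendment that edited criterion 18 for prothrombin time and hemoglobin. The ALT limit was left where it was.

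The subjects concerned are foreseeable. The GGT exception invites people with stable, lupus-related liver abnormality, and Section 7.9 names lupus hepatitis among the events common in this disease. Such a person can pass every entry criterion, start infusions and then be stopped although nothing about the liver has changed. What is at stake is avoidable exposure, an uninformative liver stopping event in the safety record, and a subject with no Week 52 efficacy assessment.

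**Working it through.** No planned figure has to be reproduced here; the check sets two sets of thresholds side by side and then counts infusions.

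**Overlap of entry and stopping limits**

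| ALT (× ULN) | Appendix 12 grade | Criterion 18 | Appendix 13 if unchanged |
|---|---|---|---|
| >2.5 to <3.0 | 2 | admitted | no stopping criterion met |
| 3.0 to <5.0 | 2 | admitted | stop once it has persisted ≥4 weeks |
| exactly 5.0 | 2 | admitted | stop once it has persisted ≥2 weeks |
| >5.0 | 3 or higher | excluded | not applicable |

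The overlap is 3.0 to 5.0 × ULN. Its upper end is a single boundary value, so in practice the conflict lies in 3 to <5 × ULN.

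**Is there a baseline exemption?** In Appendix 13, baseline appears only as an end point for monitoring and follow-up. No stopping trigger refers to it.

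**Do other criteria close the gap?** Criterion 10 covers hepatic disease not due to SLE, so it misses lupus hepatitis. Criterion 11 mentions laboratory abnormalities, but at the investigator's discretion and without a limit. Criteria 15 and 16 remove alcohol abuse and hepatitis B and C. None sets an ALT ceiling.

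**Infusions received.** The schedule is Days 0 and 14, then Day 28 to Day 336 every 28 days: 2 + [(336 − 28)/28 + 1] = 2 + 12 = 14. The protocol does not say when persistence starts to count, so for 3 to <5 × ULN:

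- From Day 0: 4 weeks are reached at Day 28. That gives 2 infusions (Days 0, 14), or 3 if Day 28 is dosed before the result is known.
- From the Day 14 test: 14 + 28 = Day 42. That gives 3 infusions (Days 0, 14, 28).
- From a screening value at least 28 days old (screening opens at Day −35): the rule is met by Day 0, giving 0 or 1.

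**Consequence for the endpoint.** Section 6.9 says subjects should be withdrawn for unacceptable toxicity, citing Section 6.8.3. Appendix 13 itself requires only the treatment stop and lets the subject stay for protocol-specified follow-up. Either way, Table 6-1 footnote A puts the Exit visit 4 weeks after the last dose. For a last dose on Day 14 or 28, that is Day 42 or 56, far outside the Day 364 ± 28 window (earliest Day 336). Section 8.5.2 then counts the subject as a nonresponder.

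**The case against.** The strongest objection is the row label. In the stopping table, the two persistence rules sit in a row labelled as an ALT increase, next to a separate row for absolute ALT (≥8 × ULN). A pre-existing, unchanged value is arguably not an increase, and Section 6.9 files the liver criteria under toxicity, which fits such a value poorly. The monitoring pathway also treats stabilisation or return to baseline as an end point, so its authors had baseline in mind. The Section 6.8.3 charts, which might settle the matter, are not reproduced.

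This stands in part. A reader might infer that the stop is mandatory beyond dispute; the documents do not support that certainty. But the text inside the cell is a plain ULN band with a duration, the monitoring pathway gives way to it, and a site following the table literally would stop the subject.

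It can also be said that a permissive entry limit with a strict stopping rule is a legitimate design: someone whose Grade 2 ALT is passing may enter, be tested weekly and complete. That is true, and it is the real cost of the change proposed. Investigator discretion under criterion 11 helps too, but criterion 18 tells the same investigator that Grade 2 is acceptable.

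A reader might further infer bias or a meaningful loss of power. Nothing supports that. The protocol gives no prevalence, the arms should be affected alike, and Section 8.4 takes its rates from trials with nearly identical eligibility, which may already include such subjects. Nor is restart strictly barred: the ALT <3 × ULN wording is part of an example, although the pathway's heading makes restart on an unchanged elevation unlikely.

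**Conclusion.** The point holds as a low-priority safety and consistency matter, with medium confidence. Criterion 18 admits ALT of 3 to <5 × ULN, and on the plain cell text of Appendix 13 an eligible subject who simply stays there is stopped after 2 to 3 of 14 infusions (0 to 3 across all readings of when persistence starts). A liver stopping event is then recorded for a pre-existing value and the subject is scored a nonresponder. This rests on reading the persistence rule by its cell text rather than its row label, and on the Appendix 13 tables without the Section 6.8.3 charts. The number affected cannot be estimated from the protocol and is probably small; the effect on the primary comparison is negligible.

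**What to change.** In criterion 18, in both Section 4.2 and the synopsis, add an exclusion for screening ALT ≥3 × ULN, and set the ALT limit in the GGT exception at <3 × ULN. AST can stay at Grade 2 or lower. Every stopping criterion in Appendix 13 requires ALT ≥3 × ULN, so no eligible subject could then meet one on an unchanged screening value. Appendices 13 and 14 stay as they are.

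The cost is a short amendment using chemistry already collected at screening. A few subjects would be lost, including some whose ALT would have fallen and who could have completed, which runs slightly against Amendment 02's aim of widening enrolment.

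The alternative is a baseline-relative stopping rule. It would keep these subjects, but it would continue dosing at ALT ≥3 × ULN and loosen a rule that Section 6.8.3 describes as aligned with regulatory liver-safety guidance. The screening limit is the smaller change.
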